3.12.3 Exploratory Efficacy Assessment

Work Productivity and Activity Impairment Questionnaire: Specific Health Problem

The Work Productivity and Activity Impairment Questionnaire (WPAIQ) is a validated 6 question assessment tool that measures time missed from work, impairment of work and regular activities due to their health problem. Subjects are asked about the effect their diabetic neuropathy has on their ability to work and perform regular activities in the past 7 days. The questionnaire will be completed by the subject at the Enrollment Visit, Month 2, and Month 4.

Biopsy

Two 3 mm punch skin biopsies will be performed at baseline and end of treatment to assess IENFD. At the Enrollment Visit, one biopsy will be obtained at the distal leg, 10 cm above the lateral malleolus on the right leg and a second biopsy will be obtained at the distal thigh, 10 cm above the superior margin of the patella on the lateral right leg. The biopsies will be shipped overnight to the University of Utah Cutaneous Nerve Laboratory. At the end of Part A study visit Month 4 (Day 121), a second set of biopsies will be obtained lateral to the baseline biopsies and shipped overnight to the central lab. Subjects who do not consent to skin biopsies may still be enrolled in the study. Subjects that did not consent to or have biopsies at the Baseline Visit may still have biopsies collected at Month 4 as they enter into the open label extension period. At the end of Part B study visit Month 12 (Day 361), a final set of biopsies will be obtained lateral to the Month 4 biopsies and shipped overnight to the central lab.

NOTE: Skin biopsies will not be performed in subjects receiving anticoagulants. Biopsies may be performed on subjects receiving anti-platelet therapy (i.e. nonsteroidal anti-inflammatory medications, clopidogrel) according to clinical judgment.

3.12.4 Additional Study Assessments

Measurement of Ankle-Brachial Index (ABI)

Ankle Brachial Index (ABI) compares pressures in the brachial arteries to lower extremity pressures in the posterior tibial and dorsalis pedis arteries as measured with doppler ultrasound. The ratio between these pressures is the ABI. Subjects should be in a supine position, with the arms and legs at the same level as the heart for a minimum of 10 minutes before obtaining the ABI measurement. ABI will be measured at the Screening Visit on both sides. For subjects that consented to having biopsies collected, ABI measurements will be taken before the biopsies are collected.

Venous Insufficiency

Venous insufficiency will be graded by the Investigator at the Screening Visit using the venous insufficiency classification scale³⁴ below:

Grade	Description
C 0	No visible changes in the clinical examination
C 1	Reticular veins, redness of the skin around the ankles
C 2	Varicose veins
C 3	Presence of edema without skin changes
C 4	Lesions dependent of venous diseases (discoloration, blemishes, lipodermatosclerosis)
C 5	Skin changes described above with signs of healed venous ulcers
C 6	Skin lesions such as in groups C1 to C4 plus active venous ulcers
$\mathbf{C} = \mathbf{C}$	linical

38

Toronto Clinical Scoring System (TCSS)

The Toronto Clinical Scoring System (TCSS) is a validated and quantitative instrument to evaluate the severity of peripheral neuropathy in the lower extremities. The scoring system is broken out into 3 elements of Reflex, Symptom, and Sensory. Each patient is assessed as to the presence or absence of symptom, reflex, or sensation on each foot. The outcome, the clinical neuropathy score, is a continuous variable ranging from a minimum of 0 (no neuropathy) to a maximum of 19 points (0-5 points no neuropathy, 6-8 points mild neuropathy, 9-11 points moderate neuropathy, and 12+ severe neuropathy). The Toronto Clinical Scoring System will be used as a screening assessment for inclusion at the Screening Visit and measured at the Day 121 visit (Month 4) and Day 361 Visit (Month 12).

Measurement of Foot Thickness

The depth of the foot (H below) will be measured from the most inferior aspect of the medial malleolus to the plantar aspect of the foot when residing on the floor (see diagram below). The depth should not be more than 8cm for inclusion in the trial for optimal treatment penetration.

The width (widest portion) and length (heel to the tip of the longest toe) of the foot will also be measured in centimeters using a tape measuring device. The shoe size will be obtained using the Brannock Foot Measuring Device.

Hemoglobin A1c (HbA1c) Test

Hemoglobin A1c provides the average level of glucose in the blood over the past 3 months. For this test, the A1C Now[®] System will be used, subjects will have a finger stick to collect 5μ L of blood to obtain the A1c value at the Screening Visit to obtain eligibility. At the end of the study, Month 4 (Day 121) the A1c will be collected and compared to the baseline

value. Each subject will have a A1C Now[®] System assigned to them. The change from baseline will be captured and assessed.

Subject adherence

Compliance with twice daily treatment with the study device will be assessed verbally during the Day 7 telephone call, at the interim visits and upon completion of the study. Data on the usage of each device is collected in real time at Regenesis Biomedical, Inc. The report will contain the patient's device treatment information and will be sent to the site at regular intervals. The site will assess compliance based on the report and contact the patient if the subject is not complying with the treatment regimen. The site will also review compliance with the subject at each of the interim visits.

Treatment Satisfaction and Blinding Assessment

Treatment satisfaction with the device will be obtained at Months 1, 2, 3, end of Part A study visit (Month 4), and at Months 8 and 12 of Part B, to assess the patients level of satisfaction with the treatment. The subject will be asked "How satisfied are you with the Investigational Treatment?" and will choose between Very Satisfied, Satisfied, Neither Satisfied or Dissatisfied, Dissatisfied, and Very Dissatisfied.

Subjects will also be asked which device (active or sham) they believe they were randomized to at the Day 7 phone call and Month 4 (Day 121) (blinding assessment).

3.12.5 Safety Assessments

Safety will be assessed through review of adverse events including serious adverse events. Adverse events will be assessed at the enrollment visit, interim visits and the Month 4 visit.

4. STUDY PROCEDURES

The study procedures are summarized in the Schedule of Events (Appendix A) and described immediately following:

4.1 Visit 1 – Screening Visit (Day -15)

The Screening Visit will take place 15 days prior to the Enrollment Visit. If a successfully screened subject falls more than 1 day early (earlier than day -14) or more than 2 days late (later than day -17), the subject will require another screening and run-in period to

participate in the trial. The following procedures will be performed during the Screening Visit:

- 1. Informed consent review and signature
- 2. Review Inclusion and Exclusion criteria
- 3. Collect Toronto Clinical Neuropathy Scoring System for Inclusion
- 4. Obtain baseline pain score (baseline score must be \geq 4 and <9 for eligibility)
- 5. Collect subject demographic data (including age, weight, height, gender, race/ethnicity)
- 6. Collect baseline diabetes related health resource utilization including the regimen for their diabetic care (number of doctors' visits and history of ulcers)
- 7. Collect Medical and Surgical History
- 8. Collect depth, width, and length foot measurements and shoe size for each foot
- 9. Conduct directed physical exam (abnormal or normal) for General Appearance, Cardiovascular, Musculoskeletal, Extremities/Skin, Neurological, and Other
- 10. Obtain Ankle-Brachial Index
- 11. Assess venous insufficiency
- 12. Measure HbA1c
- 13. Review and record medications taken for their diabetic neuropathy pain (including over the counter PRN)
- 14. Review and record all additional medications
- 15. Perform a urine pregnancy test for females of child bearing potential
- 16. If the subject meets the eligibility criteria, enroll the subject in to the 14-day ePRO run in period in the ePRO system.

During this visit, the subject will be introduced to the electronic (ePRO) diary and trained in the proper use of the patient-reported-outcome (PRO) assessment tools for pain intensity and analgesic consumption for their diabetic neuropathy pain (including over the counter and prn medications). Analgesic medications taken for their diabetic neuropathy pain will be captured in the ePRO and subjects will enter the number of pills they have taken over the last 24 hours. The ePRO diary can be accessed by the subject through any device that has an internet connection and web browser.

Subjects will be instructed to utilize their prn analgesic medications prescribed prior to enrollment in the event their diabetic neuropathy pain increases during the trial, and not to introduce new medications or therapies into their analgesic treatment regimen through Month 6 (Day 180) of the trial. In this context, "analgesic medications" includes but is not limited to nonsteroidal anti-inflammatory agents, anti-depressants and muscle relaxants, and includes medications taken on an "as needed" (prn) basis (including over the counter medications) as well as those medications taken on a regular schedule.

4.2 14-Day Run-In Period

The subject will be instructed to record NPRS scores at 8 am (\pm 2 hours) for 14 consecutive days beginning the day following the Screening Visit. There will be 2 questions generated on a daily basis, one question will address diabetic neuropathy pain and a separate question will ask the subject to enter consumption (number of pills/tablets/capsules) of each indicated analgesic taken for their neuropathic pain over the previous 24 hours.

4.3 Visit 2 – Enrollment Visit (Day 0)

The following procedures will be performed:

- 1. Review Inclusion/Exclusion criteria
- 2. Review and record any changes in medical history and study eligibility criteria since screening.
- Review average baseline NPRS score collected in ePRO (mean of the preceding 7 days must be ≥4 and <9).
- 4. Review diary compliance (must be \geq 70%)
- 5. Review analgesic pain consumption profile in ePRO
- 6. Review and record adverse events since signing of the Informed Consent
- 7. Review and record any changes in concomitant medications
- 8. Conduct Skin Perfusion Pressure (SPP)
- 9. Conduct Sural Nerve Conduction Studies (NCS)
- 10. Conduct Quantitative Sensory Testing (QST) of Cool, Warm, and Heat as Pain
- 11. Collect WPAIQ
- 12. Collect NeuroQoL
- 13. Collect Biopsies at distal thigh and distal leg from consenting subjects
- 14. If the subject continues to meet eligibility criteria, enroll and randomize subject
- 15. Introduce and train the subject on the use of the PROVANT[®] Therapy System, including instructions for proper positioning and operation of the devices.

- 16. Remind the subject in the use of patient-reported-outcome (PRO) tools of NPRS and analgesic consumption for their diabetic neuropathic pain.
- 17. Enroll the subject into the treatment period in the ePRO system.

During this visit, eligible subjects will receive a randomized Provant device and will be instructed to administer treatment on both feet twice daily at 8am and 8pm (\pm 2 hours) for 4 months (120 days).

4.4 Day 7 Phone Call (Day 7 +2 Days)

A follow-up telephone call will be performed and the following will be assessed:

- 1. Assess for adverse events
- 2. Assess for changes in concomitant medications
- 3. Assess adherence to PEMF treatment regimen and diary completion
- 4. Conduct blinding assessment
- 5. Conduct follow-up on the biopsy sites (asking the patient on how the area looks, cleaning techniques, and questions on if an infection is present) (if applicable)

4.5 1 Month Interim Visit (Day 30 ± 3 Days)

Subjects will return to the clinic on Day 30. At this visit, the following procedures will be performed:

- 1. Collect Patient Global Impression (PGI)
- 2. Assess for adverse events
- 3. Assess for changes in concomitant medications
- 4. Assess adherence to PEMF treatment regimen by reviewing the usage report provided by Regenesis Biomedical and ePRO entries
- 5. Assess treatment satisfaction

4.6 2 Month Interim Visit (Day 60 ± 3 Days)

Subjects will return to the clinic on Day 60. At this visit, the following procedures will be performed:

- 1. Collect Patient Global Impression (PGI)
- 2. Assess for adverse events
- 3. Assess for changes in concomitant medications

- 4. Assess adherence to PEMF treatment regimen by reviewing the usage report provided by Regenesis Biomedical and ePRO entries
- 5. Assess treatment satisfaction
- 6. Collect WPAIQ
- 7. Collect NeuroQoL
- 8. Conduct SPP

4.7 3 Month Interim Visit (Day 90 ± 3 Days)

Subjects will return to the clinic on Day 90. At this visit, the following procedures will be performed:

- 1. Collect Patient Global Impression (PGI)
- 2. Assess for adverse events
- 3. Assess for changes in concomitant medications
- 4. Assess adherence to PEMF treatment regimen by reviewing the usage report provided by Regenesis Biomedical and ePRO entries
- 5. Assess treatment satisfaction

4.8 4 Month End of Part A Visit (Day 121 ± 3 Days)

Subjects will return to the clinic on Day 121 for the end of Part A study visit. At this visit, the following procedures will be performed:

- 1. Assess for adverse events
- 2. Assess for changes in concomitant medications
- 3. Assess treatment satisfaction
- 4. Collect subjects weight
- 5. Collect WPAIQ
- 6. Collect NeuroQoL
- 7. Collect PGI
- 8. Conduct SPP
- 9. Conduct NCS
- 10. Conduct QST
- 11. Measure HbA1c

- 12. Obtain skin biopsies from subjects that had biopsies at baseline, or that consent to having biopsies at Month 4 as they enter the open label extension period
- 13. Collect Toronto Clinical Neuropathy Scoring System
- 14. Conduct Blinding Assessment
- 15. Assess adherence to PEMF treatment regimen by reviewing the usage report provided by Regenesis Biomedical and ePRO entries
- 16. Return of randomized device
- 17. Enroll Subject in Part B / open-label part of protocol

During this visit, subjects will receive an Active Provant device and will be instructed to administer treatment on both feet twice daily at 8am and 8pm (\pm 2 hours) for 8 months (through Day 360).

4.9 Part B - 5 Month Phone Call (Day 150 ± 3 Days)

A follow-up telephone call will be performed and the following will be performed:

- 1. Assess for adverse events
- 2. Assess for changes in concomitant medications
- 3. Assess adherence to PEMF treatment regimen

4.10 Part B - 6 Month Phone Call (Day 180 ± 3 Days)

A follow-up telephone call will be performed and the following will be performed:

- 1. Assess for adverse events
- 2. Assess for changes in concomitant medications
- 3. Assess adherence to PEMF treatment regimen and diary completion

4.11 Part B - 7 Month Phone Call (Day 210 ± 3 Days)

A follow-up telephone call will be performed and the following will be performed:

- 1. Assess for adverse events
- 2. Assess for changes in concomitant medications
- 3. Assess adherence to PEMF treatment regimen

4.12 **Part B - 8 Month Visit (Day 240 ± 3 Days)**

Subjects will return to the clinic on Day 240 for the Month 8 visit. At this visit, the following procedures will be performed:

- 1. Assess for adverse events
- 2. Assess for changes in concomitant medications
- 3. Assess adherence to PEMF treatment regimen and diary completion
- 4. Collect NeuroQoL
- 5. Collect PGI
- 6. Assess treatment satisfaction
- 7. Conduct QST

4.13 Part B - 9 Month Phone Call (Day 270 ± 3 Days)

A follow-up telephone call will be performed and the following will be performed:

- 1. Assess for adverse events
- 2. Assess for changes in concomitant medications
- 3. Assess adherence to PEMF treatment regimen

4.14 Part B - 10 Month Phone Call (Day 300 ± 3 Days)

A follow-up telephone call will be performed and the following will be performed:

- 1. Assess for adverse events
- 2. Assess for changes in concomitant medications
- 3. Assess adherence to PEMF treatment regimen and diary completion

4.15 Part B - 11 Month Phone Call (Day 330 ± 3 Days)

A follow-up telephone call will be performed and the following will be performed:

- 1. Assess for adverse events
- 2. Assess for changes in concomitant medications
- 3. Assess adherence to PEMF treatment regimen

4.16 Part B - 12 Month End of Study Visit (Day 361 ± 3 Days)

Subjects will return to the clinic on Day 361 for the end of study visit. At this visit, the following procedures will be performed:

- 1. Assess for adverse events
- 2. Assess for changes in concomitant medications
- 3. Assess adherence to PEMF treatment regimen and diary completion
- 4. Collect NeuroQoL
- 5. Collect PGI
- 6. Collect Weight
- 7. Conduct NCS
- 8. Conduct TCNSS
- 9. Conduct QST
- 10. Assess treatment satisfaction
- 11. Obtain skin biopsies from subjects that consented to having biopsies
- 12. Return of active device

4.17 Treatment adherence/study compliance

Subject adherence (compliance with twice daily treatment with the study device) will be assessed verbally during the Day 7 telephone call, at the interim visits and upon completion of the study. Data on the usage of each device is collected in real time at Regenesis Biomedical, Inc. The report will contain information on the patient's device usage and will be sent to the site at regular intervals. The site will assess compliance based on the report and contact the patient if the subject is not complying with the treatment regimen. A subject with complete adherence will be expected to have a usage report of 120 during Part A of the study and 240 during Part B of the study.

4.18 Protocol Adherence

If an investigator has deviated from the protocol in order to eliminate an immediate hazard to subjects or for other inevitable medical reasons, the investigator shall document all such deviations, including the reasons thereof, and immediately submit the documentation to the sponsor and to the IRB if required.

Deviations from the protocol including violations of inclusion/exclusion criteria will be assessed as "minor" or "major". Deviations will be defined prior to un-blinding.

4.19 Concomitant Medications

All concomitant drug and non-drug treatments as well as the frequency of administration and indication for the treatment will be recorded in the subject's chart. Additions and/or changes to the subject's therapeutic regimen (agent, dose, frequency of administration) for treatment of diabetic peripheral neuropathy pain (other than the introduction of PEMF therapy) will not be allowed through Day 360 of the study. Subjects will be allowed to continue administration of prn medications if they were added and taken at least 30 days prior to Screening.

It is important to record the reason why each analgesic is being taken by the subject, specifically analgesics taken for treatment of pain associated with diabetic neuropathy. The analgesics taken for diabetic neuropathy will be entered in to the ePRO system for the subject to enter the number of pills taken for each one daily through 120 days, at Months 5, 6, 7, 9, 10, and 11 phone calls, during the one week of ePRO assessments prior to Months 6, 8, 10, and 12 visits, and at the Month 8 and 12 on site visits. Analgesics taken for other reasons, e.g., headache, will be collected through recording of concomitant medications in the subject's chart.

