Protocol Number	RBI.2017.002
Name of Study Device	PROVANT [®] Therapy System
Phase of Development	III
Objective	To demonstrate the analgesic efficacy of PEMF treatment compared to sham treatment in patients with painful diabetic distal symmetric peripheral neuropathy (DSPN) when treatment is administered 30 minutes twice daily through a 120-day period (4 months) (Part A). An 8-month open-label active treatment extension period is included to collect longer-term data on pain, medication use, quality of life and safety (Part B).
Study Design	Part A of this trial is a multi-center, prospective, double-blinded, sham-controlled, randomized clinical trial conducted on subjects with painful diabetic distal symmetric peripheral neuropathy. Part B of this trial is an 8-month single-arm, open-label, active treatment extension period upon completion of Part A. Eligible subjects will include those between 22 and 80 years of age with documented Type 1 or Type 2 diabetes having persistent pain related to diabetic neuropathy in the lower extremities, despite previous treatment(s). Subjects will be assessed with the Toronto Clinical Neuropathy Score at screening, to evaluate the severity of peripheral neuropathy for inclusion. Eligible subjects will be entered into a 14-day ePRO diary run-in period to collect average baseline pain scores related to their diabetic neuropathy in the lower extremities, diary compliance, and analgesic consumption (maintenance and prn prescribed peripheral neuropathic pain medication pill counts). Subjects will collect electronic patient-reported outcome (ePRO) data each morning around the same time during the run-in period. Only those subjects having a mean pain intensity in the lower extremities of \geq 4 and <9 on an 11-point numeric pain rating scale (NPRS) and a diary compliance score of \geq 70% during the 14- day run-in period will be eligible. Subjects will return to the clinic at Baseline (Day 0) for review of eligibility, diary compliance, average baseline diabetic

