3.12.1 Primary Efficacy Assessment

Pain Intensity (PI)

The primary outcome measure is the absolute change in pain intensity as measured by patient reported numeric pain rating scale (NPRS) evaluations. The NPRS is a validated 11-point numerical rating scale for pain (0=no pain to 10=worst possible pain) collected as patient-reported outcomes in an electronic diary. The NPRS will be scored daily (8am \pm 2 hours) during the 14-day run-in period in order to establish a baseline for purposes of eligibility assessment. During the subsequent 4-month (120-day) treatment period, NPRS will be scored immediately after each morning treatment session (8am \pm 2 hours).

Subjects will be instructed to "Select the one number that best indicates the average intensity of pain you have had over the last 24 hours in your legs".

The primary endpoint is the absolute change from baseline in the NPRS Pain score through Month 4 (Day 120) comparing the PEMF group to the sham group. For purposes of statistical analysis, the baseline NPRS will be the average NPRS during the 7 days preceding the start of treatment with the study device. For subsequent time points, including the primary endpoint at Day 120, NPRS will be calculated as 7-day rolling averages during the treatment period.

During Part B of the protocol (through Month 12 (day 360)), NPRS will be scored immediately after each morning treatment session ($8am \pm 2$ hours) for one week prior to Months 6, 8, 10, and 12. Evaluation of the NPRS during Part B of the protocol will be considered an exploratory endpoint.

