4.19.1 Allowed Medications

Subjects will be allowed to continue their regimen of analgesic medications from the time of the Screening Visit through and including the Day 120 visit. In this context, "analgesic medications" refers to medications prescribed and administered for the treatment of pain from diabetic neuropathy, and includes but is not limited to anticonvulsants, nonsteroidal anti-inflammatory agents, anti-depressants and muscle relaxants. As such, this includes medications taken on an "as needed" (prn) basis as well as those medications taken on a regular schedule. Medications identified as those taken for the subject's painful diabetic distal symmetric peripheral neuropathy will be auto populated in the subject's ePRO diary in order to capture the number of pills/capsules/tabs taken in the last 24 hours.

Medications prescribed for other indications are allowed and will be recorded as concomitant medications.

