5. WITHDRAWAL PROCEDURES

If a subject is withdrawn from study participation, the subject's enrollment in the study will terminate, study device application will be discontinued and no further data will be collected on the subject. Efforts will be made to perform all assessments scheduled for the Month 4 Visit (Day 121) prior to subject withdrawal in Part A, and Month 12 Visit (Day 361) prior to subject withdrawal in Part B.

A subject may be withdrawn from further study participation under the following circumstances:

- At the subject's request.
- Noncompliance with the protocol by the subject.
- Adverse Event (decision to be removed from study made by either the investigator or subject). The investigator must notify the sponsor immediately if a subject is withdrawn because of an AE.
- Decision by the investigator or sponsor that termination is in the subject's best medical interest or administrative decision for a reason other than that of an AE.
- Request for withdrawal by the subject for reasons other than an intolerable AE.
- Lost to follow-up, as determined by failure to respond to at least 2 telephone calls followed by certified letter sent to the subject's last known address. All attempts to contact the subject must be documented in the subject's source documents.

6. **RISK BENEFIT**

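### The analgesic restriction ends at Day 180 in what subjects are told (Protocol 4.1) but at Day 360 in Protocol 4.19, and the two differ in scope; only the reading of the exploratory Part B data is affected.

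*Protocol*

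**What the plan says.** Three places in the protocol deal with analgesics taken for neuropathy pain.

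- **Section 4.19** (Concomitant Medications) rules that additions or changes to the regimen, whether in agent, dose or frequency, "for treatment of diabetic peripheral neuropathy pain (other than the introduction of PEMF therapy) will not be allowed through Day 360 of the study". Established prn drugs may continue.
- **Section 4.1** (Screening Visit) sets out what subjects are told. They may use their existing prn analgesics if pain increases, and are "not to introduce new medications or therapies into their analgesic treatment regimen through Month 6 (Day 180) of the trial".
- **Section 4.19.1** (Allowed Medications) says subjects are "allowed to continue their regimen of analgesic medications from the time of the Screening Visit through and including the Day 120 visit". It does not mention Part B.

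For Part B, section 3.12.1 collects the NPRS "for one week prior to Months 6, 8, 10, and 12" and adds that "Evaluation of the NPRS during Part B of the protocol will be considered an exploratory endpoint". At the Month 4 visit (section 4.8) the open-label device is handed over: "During this visit, subjects will receive an Active Provant device and will be instructed to administer treatment on both feet twice daily". That visit list checks for medication changes but neither repeats nor extends the analgesic instruction. The later Part B contacts (4.9 to 4.16) likewise only check for changes. Section 5 includes "Noncompliance with the protocol by the subject" among the circumstances in which a subject may be withdrawn. Section 4.18 grades deviations as minor or major.

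**The concern.** Sections 4.1 and 4.19 govern the same thing, the regimen for neuropathy pain, but give it different end days and different scopes. Subjects act on what they are told, and in the visit procedures (4.1 to 4.16) the Screening instruction is the only analgesic restriction passed on to them. From Day 181 a subject can keep to it and still deviate from 4.19.

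Part B is single arm and open label, so no control group offsets the effect of an added analgesic on pain. The synopsis gives Part B the purpose of gathering longer-term information that includes both pain and analgesic use. Under 4.19 the prescribed regimen behind the Month 8, 10 and 12 pain scores should be the one the subject entered with. Under 4.1 it need not be. A reader of the Part B results could not tell which rule the subjects were following, and sites would have to log deviations that their own instruction allowed.

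**Working it through.** No published figure needs reproducing here. The check is a comparison of texts and a count of days.

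**Step 1: the three texts side by side.**

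| Section | Kind of statement | What it covers | Last day |
|---|---|---|---|
| 4.1 | Instruction to subjects | New medications or therapies | 180 |
| 4.19 | Rule | Additions, and changes in agent, dose or frequency | 360 |
| 4.19.1 | Permission | Continuing the existing regimen | 120 |

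Only the first two rows restrict anything. The restriction therefore has two end days and two scopes. The third row is a separate mismatch: the stated permission to continue lapses at Day 120, while 4.19 forbids changing the regimen for a further 360 − 120 = 240 days.

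**Step 2: length of the gap.** Part B treatment runs from Day 121 to Day 360, which is 360 − 120 = 240 days. The gap between 4.1 and 4.19 is Days 181 to 360, which is 360 − 180 = 180 days. 180/240 = 75% of Part B.

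**Step 3: diary weeks in the gap.** The inputs are the contact days in 4.10, 4.12, 4.14 and 4.16 (Days 180, 240, 300 and 361, each ± 3). Each diary week is taken as the 7 days before the contact.

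| Diary week | On schedule | 3 days early | 3 days late | Wholly after Day 180? |
|---|---|---|---|---|
| Month 6 | 173–179 | 170–176 | 176–182 | No (2 days past if late) |
| Month 8 | 233–239 | 230–236 | 236–242 | Yes |
| Month 10 | 293–299 | 290–296 | 296–302 | Yes |
| Month 12 | 354–360 | 351–357 | 357–363 | Yes |

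By end day, 3 of 4 weeks lie wholly after the 4.1 instruction lapses, on schedule and at either edge of the visit window.

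**Step 4: scope.** Section 4.1 is silent on changes in dose or frequency of an existing drug at any time. By scope it is therefore narrower than 4.19 in all 4 weeks, including Month 6.

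**Step 5: Part A.** The primary endpoint uses NPRS through Day 120, which lies inside both restriction periods and inside the 4.19.1 permission. The gap in end days does not reach it.

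**Step 6: the same count after the fix.** With 4.1 running to Day 360, 0 of 4 weeks fall after its end day on schedule. If the Month 12 visit is 3 days late, Days 361 to 363 of that week still do.

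**The case against.** The case for leaving this alone has several parts.

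- **The texts can all be obeyed at once.** A subject who follows 4.19 also satisfies 4.1, and 4.19 binds sites whether or not a visit list repeats it. This is true, but subjects decide what they take, and the visit procedures give them the shorter rule.
- **Other material may close the gap.** The synopsis has subjects re-consented for Part B if this was not done earlier, and the SAP places the Part B analysis in a separate document. Neither the consent text nor that SAP was available, so what subjects were told is known only from the protocol. This limit stands. Even clear consent wording would leave 4.1 and 4.19 in conflict.
- **An added analgesic would be seen.** Section 4.19 collects neuropathy analgesic pill counts at the Part B calls, in each diary week and at the Month 8 and 12 visits. This stands and lowers the impact. Recording does not settle whether a change was a deviation.
- **Analgesic intake varies anyway.** Existing prn use is permitted, so aligning the dates would not give pain scores on constant intake. This also stands: what 4.19 holds fixed is the prescribed regimen.

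Two stronger readings are tempting. A reader might infer that 4.19.1 sets a third end day at Day 120. It does not, because it permits continuation and restricts nothing. A reader might also infer that some sites will withdraw subjects for a post-Day-180 change while others keep them. Section 5 says only that a subject may be withdrawn, and section 4.18 already grades deviations. Divergent handling is possible, but the documents do not show that it would happen.

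**Conclusion.** The conflict is real and minor. Sections 4.1 and 4.19 give the same restriction two end days, 180 days apart, and two scopes; 4.19.1 separately stops a permission too early. The 3-of-4 count applies to end day only. By scope the shortfall covers all four Part B diary weeks.

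The consequence is confined to how single-arm Part B pain and medication-use data can be read, and to avoidable deviations. The Part A comparison stands, and Part B NPRS is exploratory.

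A reader might want to turn this into points of bias on the NPRS by multiplying a share of subjects who add a drug by an effect per subject. The documents supply neither quantity, so no such figure is given.

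The conclusion assumes that the protocol's visit procedures reflect what sites tell subjects and that the unseen consent text does not already correct it.

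**What to change.** 1. In 4.1, change the end day to Day 360 (the end of Part B) and use the 4.19 scope: no additions and no changes in agent, dose or frequency, with existing prn use allowed.
2. In 4.19.1, extend the permission to continue existing analgesics to Day 360.
3. Add the instruction to the Month 4 visit list in 4.8, at the point where the open-label device is dispensed.
4. For subjects already told Day 180, correct the instruction at the next contact. Under 4.18, class any Day 181–360 change made before that contact as a minor deviation.

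The Part A analysis needs no change. The cost is wording in two sections, one line in the Month 4 list, a short deviation rule and brief re-instruction of enrolled subjects. No new data or analyses are needed.
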